Participants who die due to any cause without a documented objective disease progression will be considered to have progressed on the date of their death. Participants who do not have any post-Baseline tumor assessments will be censored on the date of their first dose of study treatment. Participants who discontinue early from Part A or discontinue study treatment without documented objective disease progression or death, will be censored on the date of their last available (scheduled or unscheduled) tumor assessment at which a lack of objective disease progression was determined. Participants who start anti-cancer therapy during Part A without a prior documented objective disease progression will be censored on the date of their last available (scheduled or unscheduled) tumor assessment prior to the initiation of the subsequent anti-cancer therapy. If anti-cancer therapy starts on the same date as the participant's tumor assessment and determination of objective disease progression, or the participant's death (due to any cause), then the participant will not be censored and the participant will be included as having an uncensored event on this date. This censoring rule will also be applied to participants who are ongoing at any data cut-off for an analysis of Part A data who have no documented objective disease progression. The use of anti-cancer therapy during Part A will be identified via ongoing medical review of the concomitant medications together with the start dates of further anti-cancer therapy information recorded on the survival follow-up pages of the eCRF.

As a sensitivity analysis, PFS will also be calculated as the time in days from the first dose of study treatment to the date of the first documented objective disease progression (per RECIST 1.1), the date of clinical disease progression, as determined by the investigator, or the date of death due to any cause, whichever occurs first. Last contact date (as defined above for DOR) will be used for the censoring of participants still alive with no reported disease progression

(objective or clinical). The same rules described above for the censoring of participants who start anti-cancer therapy will be applied in this sensitivity analysis.

Further details on the derivation of PFS are included in the Derivation of Efficacy Endpoints document Version 0.6 (dated 21 January 2022).

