Progression-free survival (PFS) will be calculated as the time in days from the first dose of study treatment to the date of the first documented objective disease progression (i.e. according to the RECIST guidelines), or death due to any cause, whichever occurs first. The following calculation will be performed:

$$PFS = (\text{Date of Objective Progressive Disease/Death} - \text{Date of First Dose}) + 1$$

Participants who die due to any cause without a documented objective disease progression will be considered to have progressed on the date of their death. Participants who do not have any post-Baseline tumor assessments will be censored on the date of their first dose of study treatment. Participants who discontinue early from Part A1 or discontinue study treatment without documented objective disease progression or death, will be censored on the date of their

last available (scheduled or unscheduled) tumor assessment at which a lack of objective disease progression was determined. Participants who start anti-cancer therapy during Part A1 without a prior documented objective disease progression will be censored on the date of their last available (scheduled or unscheduled) tumor assessment prior to the initiation of the subsequent anti-cancer therapy. If anti-cancer therapy starts on the same date as the participant's tumor assessment and determination of objective disease progression, or the participant's death (due to any cause), then the participant will not be censored and the participant will be included as having an uncensored event on this date. This censoring rule will also be applied to participants who are ongoing at any data cut-off for an analysis of Part A1 data who have no documented objective disease progression. The use of anti-cancer therapy during Part A1 will be identified via ongoing medical review of the concomitant medications together with the start dates of further anti-cancer therapy information recorded on the survival follow-up pages of the eCRF.

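### The sensitivity PFS counts clinical progression as an event but reuses a new-therapy censoring rule keyed to objective progression only, and gives no precedence between the two

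*SAP*

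**What the plan says.** **Event definition.** Section 10.1.1 of each SAP (Part A and Part A1) defines the sensitivity PFS as running from first dose to the earliest of objective progression, "the date of clinical disease progression, as determined by the investigator, or the date of death due to any cause, whichever occurs first".

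**Therapy rule in the main analysis.** Part A: "Participants who start anti-cancer therapy during Part A without a prior documented objective disease progression will be censored" at the last "tumor assessment prior to the initiation of the subsequent anti-cancer therapy". Part A1 has the same rule: "Participants who start anti-cancer therapy during Part A1 without a prior documented objective disease progression will be censored on the date". The exception for therapy starting on the day of an event covers therapy that begins "on the same date as the participant's tumor assessment and determination of objective disease progression", or on the day of death. Clinical progression appears in neither place.

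**Therapy rule in the sensitivity analysis.** Both SAPs carry it over in one sentence: "The same rules described above for the censoring of participants who start anti-cancer therapy will be applied in this sensitivity analysis".

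**Neighbouring rule.** The sentence just before it was rewritten for the wider event: "Last contact date (as defined above for DOR) will be used for the censoring of participants still alive with no reported disease progression", followed by a bracket that names both objective and clinical progression.

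**Further detail.** Both SAPs refer additional PFS derivation rules to the Derivation of Efficacy Endpoints document, Version 0.6, which is not among the documents at hand.

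**The concern.** The only difference in event definition between the two PFS analyses is that clinical progression counts in the sensitivity version. The DOR text in Section 10.1.1 says clinical progression is recorded as a reason for stopping study treatment, so another therapy may well follow. These are the participants on whom the two PFS analyses should differ, and the imported rule can return them to the main-analysis result: censored at a scan taken before the clinical progression. Such censoring is informative, because it is triggered by a course that includes the worsening itself.

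At stake is whether the comparison of main and sensitivity PFS can be read at face value. Section 10.1.2 repeats for the sensitivity analysis the event and censoring counts, Kaplan-Meier quartiles, 3-, 6- and 9-month rates and curves, all by treatment group. Groups are small (3 to 6 evaluable participants per Part A cohort, up to 8 per Part A1 cohort), so one reclassified participant can be visible. Two programmers could also derive different datasets from the same text.

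**Working it through.** The SAPs state no PFS event count or power, so there is no figure to reproduce. The check puts hypothetical participants through the rules.

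**Inputs.** PFS in days = (event or censoring date − first dose date) + 1, so PFS time equals study day. In Part A the first scan is targeted at Cycle 2 Day 22 (Section 10.1.2), which is 28 + 22 = Day 50. All other days are illustrative.

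**Two derivations.**
- *Censoring rule followed literally:* if new therapy starts and there is no objective progression on or before that date (and no death that day), censor at the last scan before therapy. Otherwise take the earliest event.
- *Rule keyed to objective or clinical progression:* censor for new therapy only if no objective progression, clinical progression or death occurred on or before its start. Otherwise take the earliest event.

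| Last scan before progression | Clinical progression | Objective progression | New therapy | Literal rule | Rule keyed to both |
|---|---|---|---|---|---|
| Day 50 | Day 85 | none | Day 95 | censored Day 50 | event Day 85 |
| Day 50 | Day 70 | none | Day 70 | censored Day 50 | event Day 70 |
| Day 50 | Day 70 | none | none | event Day 70 | event Day 70 |
| Day 50 | Day 70 | Day 80 | Day 85 | event Day 70 | event Day 70 |

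In row 1 the event is lost and follow-up is cut by 85 − 50 = 35 days. The main analysis also censors this participant at Day 50, so the two analyses agree by construction. Row 2 shows that the same-day exception does not help. Rows 3 and 4 show who is unaffected: clinical progressors with no new therapy, or with objective progression before it.

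**Comparison with DOR.** The DOR sensitivity text in Section 10.1.1 states no new-therapy censoring rule. If the row 1 participant had an unconfirmed partial response at Day 50, the DOR sensitivity analysis would record an event with duration 85 − 50 + 1 = 36 days. The PFS sensitivity analysis, under the literal rule, would censor at Day 50. The same progression would count in one and not in the other.

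**Size, on assumed rates only.** Let c be the share of participants who progress clinically only and f the share of those who start new therapy. Expected events lost among 42 participants (the Part A maximum, SAP Section 2.4) are 42 × c × f:
- c = 10%, f = 25%: 42 × 0.10 × 0.25 = 1.05
- c = 30%, f = 75%: 42 × 0.30 × 0.75 = 9.45

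A simulation used exponential progression times with a median of about 60 days, scans at Day 50 and every 56 days after, new therapy 5 to 29 days after clinical progression, and 400 repetitions. Mean events fell from 42 to 41.0 and 32.9 at those two settings. Mean 3-month PFS rose from 0.547 to 0.558 and from 0.501 to 0.603. These rates place participants with no scan before therapy at Day 1, which the SAP does not state for this analysis. Rerunning with those participants keeping their events gave 0.552 and 0.546, so the rise was about 0.5 and 4.5 points instead of about 1 and 10.

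**The case against.** The strongest reply is that the plan leaves a conflict open and does not fix a wrong rule. The same paragraph takes whichever event comes first and reserves last-contact censoring for people with neither kind of progression. A programmer could let that event definition prevail, or read the imported rules as adapted to the wider event. The Derivation of Efficacy Endpoints document may say so. This stands as a limit on certainty. It does not remove the conflict, because the adjoining last-contact sentence was adapted in words and the therapy sentence was not.

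Three stronger readings are tempting and are not supported:

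- *Early clinical progressors are censored at first dose.* The first-dose rule is a separate sentence for participants with no post-Baseline tumor assessment. Whether it carries into the sensitivity analysis is not stated. A scan may also exist before therapy: the Part A SAP assigns scans on Days 47 to 58 even for people who stop before Cycle 2 (Section 10.1.2), and refers to assessments at the safety follow-up visit (Section 4.3).
- *A large share of a cohort loses its events.* No document gives a rate of clinical-only progression followed by new therapy.
- *Any agreement between main and sensitivity PFS is an artefact.* Clinical progressors outside the affected path keep their events, so agreement could be genuine. Nor does the paragraph state a purpose for the analysis that the rule could be said to contradict; it gives an event definition and censoring rules.

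It is also fair that the stakes are low. Antitumor activity is exploratory in both parts, PFS is summarized descriptively and only if the data allow, and the escalation criteria in the Part A SAP do not use it.

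**Conclusion.** The point holds as a conflict within the text of both SAPs. A participant with clinical progression and no objective progression before new therapy satisfies the event definition and the censoring rule at once, with no stated precedence. Applying the censoring rule replaces the event with censoring at an earlier scan and biases sensitivity PFS upward, toward the main analysis.

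The effect is confined to that path, and its size cannot be known from the documents. The simulated range depends on assumed rates and on how participants without a scan are handled, so it shows direction and rough scale only. The conclusion assumes that the derivation document does not already settle precedence. Given an exploratory endpoint and a secondary analysis of it, this is worth correcting before database lock but affects no decision rule in the SAPs.

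**What to change.** In Section 10.1.1 of both SAPs, replace the sentence that carries the therapy rule over with text to this effect: *For the sensitivity analysis, a participant who starts anti-cancer therapy with neither objective nor clinical progression on or before the start date is censored at the last tumor assessment before that therapy, unless death occurs on the start date. Clinical progression on or before the start date counts as an event on its own date unless an earlier event has occurred.* This extends the same-day exception to clinical progression. Bring the Derivation of Efficacy Endpoints document into line, and update the SAP version reference if that document changes.

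The cost is a short text change in each SAP, the matching analysis-dataset derivation and a check of the derivation document. No new data are needed: the date of clinical progression is already part of the treatment discontinuation listing (Section 5.1), and therapy start dates come from the concomitant medication review and survival follow-up pages (Section 10.1.1).

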10.1.2 Analysis of the antitumor activity endpoints

The analyses of the antitumor activity endpoints in Part A will be performed for the PPS. As a sensitivity analysis, all analyses will be repeated for the SS. All listings will be presented for the SS. Summaries and listings will be presented by treatment group.

All lesion assessment data recorded at Baseline and during the Treatment Period (during every even cycle of study treatment) will be listed separately for target lesions, non-target lesions and new lesions. These listings will include lesion number and lesion type (nodal/non-nodal), location, method of assessment, dimension (or an indication that the lesion is too small to measure, for target lesions only) and lesion response evaluation (for non-target lesions at post-Baseline assessments). The listing for target lesions will also include the derived eCRF component data used for the determination of the overall target lesion response at each post-Baseline assessment (e.g. sum of all dimensions across target lesions and percentage change from Baseline in the sum). In addition, the overall response assessment for target lesions and non-target lesions, as determined by the investigator, will be listed together with the presence of new lesions and the investigator's overall tumor response assessment.

The investigator's overall tumor response assessment will be summarized using frequency counts and percentages by visit (tumor assessment). For the purpose of this summary, post-Baseline tumor assessments (scheduled or unscheduled but excluding tumor assessments performed at the SFU visit) will be assigned to the targeted Day 22 visit of each even cycle of study treatment using the protocol-defined window of Day 21 to 28 (± 2 days). For participants who receive 2 or more cycles of study treatment, post-Baseline tumor assessments that were performed on Day 19 to Day 30 relative to Day 1 of each even cycle will be included as Cycle 2/4/6/8 etc. Day 22 assessments. For participants who discontinue study treatment prior to the start of Cycle 2, post-Baseline tumor assessments that were performed on Day 47 to 58 relative to Day 1 of Cycle 1 will be included as a Cycle 2 Day 22 assessment. Otherwise, the tumor assessment will be classified as an unscheduled assessment and not included in the summary of overall tumor response.

Bar charts will also be produced for overall tumor response rate by treatment group for each visit. In addition, waterfall plots of participants' percentage change from Baseline in the sum of dimensions for all target lesions will be presented by treatment group and visit. The individual participants' bars will be colored by overall tumor response at the visit.

Confirmed BOR and unconfirmed BOR for each participant will be derived programmatically using the investigator's overall tumor response assessments (scheduled and unscheduled) performed between Days 21 and 28 of Cycle 2 and each subsequent even cycle of study treatment and the RECIST criteria. Whether a BOR of CR or PR is confirmed or unconfirmed will be indicated on this listing. Using a participant's confirmed BOR and unconfirmed BOR, whether the participant achieves an objective tumor response (i.e. a BOR of CR or PR) and/or disease control (i.e. a BOR of CR, PR or SD) during study treatment will be determined based on both confirmed BOR and unconfirmed BOR. These derived data will be listed for the SS.

Confirmed BOR and unconfirmed BOR will be summarized using frequency counts and percentages. Bar charts will also be produced for confirmed BOR and unconfirmed BOR by treatment group.

The number and percentage of participants achieving objective tumor response and disease control (ORR and DCR) based on confirmed BOR and unconfirmed BOR will be presented and, if data allow, exact 95% confidence intervals for binomial proportions will be calculated using the Clopper-Pearson method and presented for the response rates. In the calculation of ORR and DCR, the denominator will include all participants in the analysis set. Objective response rate and DCR (based on confirmed BOR and unconfirmed BOR) will also be summarized in bar charts by treatment group overall and by tumor type and ECOG performance status at Baseline.

In addition, waterfall plots of each participant's best percentage change from Baseline in the sum of the dimensions for all target lesions will be presented by treatment group overall and by tumor type and ECOG performance status at Baseline with the individual participants' bars colored by confirmed BOR and unconfirmed BOR.

The summaries and analyses of DOR, PFS and OS will be carried out as described below, if the data allow.

Duration of confirmed response, duration of unconfirmed response and PFS will be listed and summarized descriptively using Kaplan-Meier estimation. These summaries will be repeated for the sensitivity analyses of these endpoints (defined in Section 10.1.1 above) and will include the number and percentage of participants with the event, the number and percentage of participants censored, minimum and maximum values and Kaplan-Meier estimates of the 25th percentile, median, 75th percentile and corresponding 95% CIs calculated using Greenwood's formula. In addition, DOR and PFS rates at specific timepoints (3 months, 6 months, 9 months) will be derived from the Kaplan-Meier estimation and presented together with associated 95% CIs.

Kaplan-Meier curves will be presented for duration of confirmed response, duration of unconfirmed response and PFS, and for the associated sensitivity analyses. Treatment groups will be overlaid on each plot.

Survival status collected on the eCRF at the SFU visit and at the Final Visit will be listed for each participant by treatment group. This listing will include the participant's survival status,

date and cause of death, whether an autopsy was performed and date of autopsy, whether the participant had received any further antitumor treatment after the last dose of study treatment and the type of treatment, and whether the participant's disease had been assessed since the end of study treatment including method of assessment and the overall response.

Overall survival times will be listed and summarized descriptively using Kaplan-Meier estimation. Note that since participants are only followed up for survival until the Final Visit in Part A of the study, a summary of OS may not be meaningful (i.e. if no participants die then OS cannot be assessed).

Additional exploratory analyses of selected antitumor activity endpoints may be performed based on subgroups of participants in the SS.

Additionally, the relationship of the antitumor activity variables with key PK parameters may be explored but this will be reported separately.

10.2 ECOG performance status

ECOG performance status is an additional efficacy assessment performed in Part A of this study and is defined in Table 10-1.

Table 10-1: ECOG Performance Status Scale

Grade	ECOG performance status scale
0	Fully active, able to carry on all pre-disease performance without restriction
1	Restricted in physically strenuous activity but ambulatory and able to carry out work of a light or sedentary nature (e.g. light housework, office work)
2	Ambulatory and capable of all self-care but unable to carry out any work activities. Up and about more than 50% of waking hours
3	Capable of only limited self-care, confined to bed or chair for more than 50% of waking hours
4	Completely disabled. Cannot carry out any self-care. Totally confined to bed or chair
5	Dead

ECOG=Eastern Cooperative Oncology Group.

ECOG performance status will be listed by treatment group at each visit together with changes from Baseline for the SS.

ECOG performance status will be summarized as an ordinal categorical variable using frequency counts and percentages. Shift tables for the change from Baseline in each grade will be summarized by visit.

11 OTHER ANALYSES

Not applicable.

13 APPENDICES

13.1 SMQ algorithm for identification of anaphylactic reactions

Based on MedDRA Version 25.1, the SMQ=‘Anaphylactic reaction’ consists of 3 parts:

1) A **narrow search** containing PTs that represent core anaphylactic reaction terms:

Category A

Anaphylactic reaction

Anaphylactic shock

Anaphylactic transfusion reaction

Anaphylactoid reaction

Anaphylactoid shock

Circulatory collapse

Dialysis membrane reaction

Kounis syndrome

Procedural shock

Shock

Shock symptom

Type I hypersensitivity

2) A **broad search**:

Category B

Acute respiratory failure
Asthma
Bronchial oedema
Bronchospasm
Cardio-respiratory distress
Chest discomfort
Choking
Choking sensation
Circumoral oedema
Cough
Cough variant asthma
Cyanosis
Dyspnoea
Hyperventilation
Irregular breathing
Laryngeal dyspnoea
Laryngeal oedema
Laryngospasm
Laryngotracheal oedema
Mouth swelling
Nasal obstruction
Oedema mouth
Oropharyngeal oedema
Oropharyngeal spasm
Oropharyngeal swelling
Pharyngeal oedema
Pharyngeal swelling
Respiratory arrest
Respiratory distress
Respiratory failure
Reversible airways obstruction

This document cannot be used to support any marketing authorization
PUBLIC COPY
and any extensions or variations thereof.

Sensation of foreign body
Sneezing
Stridor
Swollen tongue
Tachypnoea
Throat tightness
Tongue oedema
Tracheal obstruction
Tracheal oedema
Upper airway obstruction
Vaccine associated enhanced respiratory disease
Wheezing

Category C

Allergic oedema
Angioedema
Circumoral swelling
Erythema
Eye oedema
Eye pruritis
Eye swelling
Eyelid oedema
Face oedema
Flushing
Injection site urticaria
Lip oedema
Lip swelling
Nodular rash
Ocular hyperaemia
Oedema
Oedema blister
Periorbital oedema
Periorbital swelling

This document cannot be used to support any marketing authorization application and any extensions or variations thereof.

PUBLIC COPY

Pruritis

Pruritis allergic

Rash

Rash erythematous

Rash pruritic

Skin swelling

Swelling

Swelling face

Swelling of eyelid

Urticaria

Urticaria papular

Category D

Blood pressure decreased

Blood pressure diastolic decreased

Blood pressure systolic decreased

Cardiac arrest

Cardio-respiratory arrest

Cardiovascular insufficiency

Diastolic hypotension

Hypotension

Hypotensive crisis

Post procedural hypotension

Note that if the MedDRA version is increased from 25.1 during the study, any changes to the terms in the above categories should be applied.

The following **algorithmic approach** will be applied: A or (B and C) or [D and (B or C)], i.e.

If a participant has a TEAE which codes to a PT included in Category A, then the event will be flagged as an anaphylactic reaction. Note that participants with a TEAE coded to a PT='Type 1 hypersensitivity' will also be flagged as having a hypersensitivity reaction as this PT is also included in the Category A narrow search for the 'Hypersensitivity' SMQ.

OR

If a participant has a TEAE which codes to a PT included in Category B **AND** has a TEAE which codes to a PT included in Category C, **and both TEAEs have the same start date**, then both events will be flagged as anaphylactic reactions.

OR

If a participant has a TEAE which codes to a PT included in Category D **AND** has (either a TEAE which codes to a PT included in Category B **OR** a TEAE which codes to a PT included in Category C), **and both TEAEs have the same start date**, then both events will be flagged as anaphylactic reactions.

